7.4.2 Analysis of the Secondary Endpoint(s)

Summaries and analysis of acceptability variables will be presented for both the modified and per-protocol study populations.

Device use and protocol procedures compliance rates will be calculated and presented.

A device acceptability source document has been created and provided to DCAC for database build and e-CRF production. Descriptive statistics for each variable will be calculated and presented.

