5.5.3 Investigator Decision to Discontinue Subject Use of Device

A subject may be removed from the study for the following reasons post initial device use; however, whenever possible the subject should be followed for safety evaluations per protocol:

- Study non-compliance to protocol requirements that in the opinion of the participating clinical site PI or appropriate sub-investigator poses an increased risk (e.g., missing safety labs) or compromises the validity of the data.

- Lost to follow-up. (*A subject will be considered lost to follow-up if he or she fails to appear for a follow-up assessment. Extensive effort (i.e., generally three documented contact attempts via telephone calls, e-mail, etc., made on separate occasions) will be made to locate or recall the subject, or at least to determine the subject's health status. These efforts will be documented in the subject's study file.*)
- Medical disease or condition, or new clinical finding(s) for which continued participation, in the opinion of the participating clinical site PI or appropriate sub-investigator, might compromise the safety of the subject, interfere with the subject's successful completion of this study, or interfere with the evaluation of safety.
- If any AE, clinical laboratory abnormality or situation occurs such that continued participation in the study would not be in the best interest of the subject.
- The occurrence of a SAE.
- If the subject is using the device in any manner inconsistent with instructions and protocol directives and procedures.

If the subject agrees, every attempt will be made to follow all AEs through resolution or stabilization.

Subjects who withdraw, or are withdrawn from this study, or are lost to follow-up after signing the informed consent form (ICF) and use of the RD19 device will not be replaced. Subjects who withdraw, or are withdrawn from this study, or are lost to follow-up after signing the ICF but before use of the device may be replaced.

The reason for subject discontinuation or withdrawal from the study will be recorded on the appropriate e-CRF.

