- All subjects will complete a brief survey of device tolerability and acceptability. This will be completed during the 60 minute follow-up period after device use in the clinic.

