7.3 Populations for Analyses

The full safety analyses population is by intention-to-treat (ITT) including all subjects who received at least a single use of RD19.

A modified per protocol population for analyses will include all study volunteers who complied with study procedures and remained on study, per protocol, until at least the day 7 clinic visit.

The per protocol population for analyses will include all study volunteers who complied with all protocol procedures and remained on the study until their day 14 visit.

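### Acceptability is summarised only in the two sets selected on compliance and retention; the existing at-least-one-use set should carry the main summary (minor)

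*Combined protocol and SAP*

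**What the plan says.** Section 7.4.2 sets the population for the secondary endpoint: "Summaries and analysis of acceptability variables will be presented for both the modified and per-protocol study populations". Two further sentences there name no population: "Device use and protocol procedures compliance rates will be calculated and presented" and, after a reference to the acceptability source document, "Descriptive statistics for each variable will be calculated and presented".

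Section 7.3 defines three sets.
- Safety: the set is described as "including all subjects who received at least a single use of RD19".
- Modified per-protocol: "A modified per protocol population for analyses will include all study volunteers who complied with study procedures and remained on study", with retention required to at least the Day 7 visit.
- Per-protocol: "study volunteers who complied with all protocol procedures and remained on the study until their day 14 visit".

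On data collection, Section 6.2 says: "All subjects will complete a brief survey of device tolerability and acceptability". The survey is done in the hour after in-clinic device use, and Table 3 (Section 1.2) marks it on Day 1, Day 7 and Day 14/early termination. Section 1.1.2 defines the secondary endpoint as ease of use, clarity of instructions, compliance with the schedule and reasons for non-compliance. Section 5.5.3 lists among the grounds for removal: "If the subject is using the device in any manner inconsistent with instructions and protocol directives and procedures".

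**The concern.** The survey is collected from everyone who uses the device, but the planned summaries keep only those who complied and stayed. A person who struggles with the device or finds the instructions unclear may be more likely to deviate, to be removed for incorrect use, or to leave in the first week. If so, the answers most informative about ease of use and clarity are the ones left out, and acceptability looks better than it was.

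What is at stake is how acceptability is reported. Section 7.1 says that the study tests no hypothesis, and no decision rule in the documents uses this endpoint. Section 7.4.1 assigns the safety summaries in general to the safety population, so the main safety description does not depend on this choice.

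**Working it through.** The plan gives no acceptability figure, so there is nothing to reproduce. The check compares the set definitions with the survey schedule and then bounds the effect.

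**Inputs.** N = 25 (Sections 1.1.4 and 4). Users who leave after device use are not replaced (Section 5.5.3). No exclusion or non-compliance rate is given; Section 7.2 assumes only that subjects will likely complete. Assumed here: each survey item can be scored favourable or not, and all 25 users answer on Day 1.

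**Step 1: who is in which set.**

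| User | Day 1 survey due | Modified per-protocol | Per-protocol | At least one use |
|---|---|---|---|---|
| Complies, stays to Day 14 | yes | in | in | in |
| Complies, leaves after the Day 7 visit | yes | in | out | in |
| Complies, leaves before Day 7 | yes | out | out | in |
| Judged non-compliant | yes | out, but no threshold is stated | out | in |

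Only the last two rows are lost from both planned summaries. Section 7.3 gives no compliance threshold for the modified set, so the last row could hold nobody or many.

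**Step 2: bound at Day 1.** Let k users be excluded, with favourable rate p_exc, and let p_ret be the rate among the 25 − k retained.

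All-user rate = [(25 − k) × p_ret + k × p_exc] / 25

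Overstatement = p_ret − all-user rate = (k/25) × (p_ret − p_exc)

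If p_exc is no larger than p_ret, this lies between 0 and k/25:
- k = 1: at most 1/25 = 4 points
- k = 2: at most 2/25 = 8 points
- k = 3: at most 3/25 = 12 points

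The maximum needs every retained user favourable and every excluded user unfavourable. For k = 2 the restricted set would then show 23/23 = 100% and the all-user set 23/25 = 92.0%. If p_exc exceeds p_ret, the sign changes and the restricted set understates acceptability.

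**Step 3: a less extreme example (assumed).** Take k = 2, with 18 of the 23 retained users favourable. The restricted set shows 18/23 = 78.3% (exact 95% CI 56.3 to 92.5).

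| Favourable among the 2 excluded | All users | Exact 95% CI | Restricted minus all-user |
|---|---|---|---|
| 0 | 18/25 = 72.0% | 50.6 to 87.9 | +6.3 points |
| 1 | 19/25 = 76.0% | 54.9 to 90.6 | +2.3 points |
| 2 | 20/25 = 80.0% | 59.3 to 93.2 | −1.7 points |

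Each shift is small against the width of the intervals.

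**Step 4: compliance rate.** Section 7.4.2 gives neither a population nor a denominator. Two sessions a day over Days 1 to 14 would be 2 × 14 = 28. Day 14 is the final visit, and Sections 5.3.1 and 5.5.2 require the device back when participation ends, so a second Day 14 session may not be possible. If it is not, a subject who does everything possible would score 27/28 = 96.4% on a denominator of 28.

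**The case against.** The strongest case for leaving the plan alone has four parts.

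- **Few exclusions are expected.** Section 7.2 assumes that subjects will likely complete a short study. That assumption covers completing the trial and safety visits. It does not cover compliance, on which both sets are also selected.
- **The selection is visible.** Section 7.4.3 reports absolute numbers and ratios of enrolled to modified per-protocol and to per-protocol, and Section 5.5.3 requires the reason for discontinuation to be recorded. This stands: a reader can see how many were excluded and apply the bound. It does not show how those users rated the device.
- **The closing sentence on descriptive statistics could cover all users.** It names no population, so it cannot be relied on to restore those whom the population sentence leaves out.
- **The endpoint is secondary and descriptive, and the likely shifts are smaller than the sampling uncertainty.** This stands and sets the rating.

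Two stronger readings are tempting. A reader might infer that everyone who stops early disappears from the acceptability results. The documents do not support that: the modified set asks for retention only to Day 7, and Section 5.5.4 says that stopping device use is not the same as leaving the study. A reader might also infer that the compliance rate would be 100% by construction. That would follow only if the per-protocol set were used for it and its definition applied literally, and nothing in Section 7.4.2 says that it will be used. What is missing there is a definition.

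**Conclusion.** The point holds and is minor. As written, users who leave before Day 7 or are judged non-compliant are absent from both planned acceptability summaries, although their Day 1 answers should exist and a suitable all-user set is already defined. No other section plans an all-user acceptability summary.

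The bound in Step 2 rests on all 25 users answering on Day 1 and on excluded users being no more favourable than retained ones. A reader might conclude that acceptability will be overstated; the documents do not establish that, because they give neither the number excluded nor the direction of their answers. Compliance is a request for clarification only.

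**What to change.** In Section 7.4.2, replace the population sentence with:

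> The main summary of acceptability variables will include all subjects with at least one use of RD19 (Section 7.3), by visit (Day 1, Day 7, Day 14/early termination), with the number of respondents at each visit. Modified per-protocol and per-protocol summaries are supportive.

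As a clarification, state that compliance rates and reasons for non-compliance are summarised in the same all-user set. The sponsor should define the number of scheduled sessions, including whether a second Day 14 session is possible given device return, and how sessions after withdrawal or during a study pause are counted.

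**Cost.** The acceptability change is wording only: the population exists and the surveys are already scheduled. Reported acceptability may be slightly less favourable. The all-user comparison is assured only at Day 1, because Section 5.5.2 makes the early-termination visit voluntary and later surveys may be missing for those who leave. For compliance, the sponsor should check that missed sessions and their reasons are captured. The diary review in Section 6.2 mentions only adverse events, serious adverse events and concomitant medications, and the acceptability source document is not among the documents available.

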1.1.2 Objectives and Endpoints

Table 1: Objectives and Endpoints (Outcome Measures)

| OBJECTIVES | ENDPOINTS (OUTCOME MEASURES) |
|------------|--|
| Primary | 
Evaluation of the safety and reactogenicity of the RD19 device. 
Frequency, grade and attribution of each incident local and systemic AE during the 14 day study period.Frequency and attribution of any incident SAEs during the 14 day study period. |
| Secondary | 
Evaluation of the acceptability of the EmitBio™ RD19 device. 
Ease of use, clarity of user instructions, & compliance with per protocol schedule and, if out of compliance, reason(s) for non-compliance. |

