7.4 Statistical Analyses

7.4.1 Primary Safety Analyses

Summaries and analyses of safety data will be presented for the Safety Analysis Population.

Solicited AEs will be summarized overall and by maximum severity post through study day 7, post study period days 7 -14 and overall. Additionally, solicited AEs will be analyzed by taking the most severe response (grouped as either modified per protocol or per protocol), dichotomizing into a binary variable (none versus mild, moderate, or severe) and using standard techniques, such as exact confidence intervals (CI), to summarize the proportion of subjects reporting each solicited sign or symptom.

Unsolicited non-serious AEs will be collected from the time of first device use through study day 14. Unsolicited AEs will be coded by MedDRA™ for preferred term and system organ class (SOC). All SAEs will be collected from the time of first device use through the study day 14. The number of SAEs will be reported by detailed listings showing the event description, MedDRA™ preferred term and SOC, study day of occurrence, severity, relatedness, and outcome for each event. Non-serious unsolicited AEs will be summarized as number and percentage of subjects reporting at least one event in each MedDRA□ preferred term and SOC, cross tabulated by severity and relationship to the study device. Additionally, the proportion of subjects and exact 95% CIs of AEs in aggregate and by MedDRA□ categories will be computed.

Clinical laboratory data, including methemoglobin measurements, will be summarized by severity and as the maximum numeric value over the entire study. Graphical presentations may include box plots and shift plots.

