7.4.3 Baseline Descriptive Statistics

Summaries of demographic variables such as age, sex, ethnicity, and race will be presented. Summaries of baseline clinical laboratory values will be presented.

Absolute numbers and ratios of Screened:Enrolled, Enrolled:Modified Per-Protocol and Enrolled:Per-Protocol will be presented.

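### Acceptability is summarised in sets selected for compliance and retention, so early leavers' data are collected but left out of one or both stated summaries

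*Combined protocol and SAP*

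**What the plan says.** Table 1 (section 1.1.2), repeated in 3.2, makes acceptability the secondary endpoint: ease of use, clarity of the instructions, and "compliance with per protocol schedule and, if out of compliance, reason(s) for non-compliance".

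Section 7.4.2 assigns the acceptability variables to two sets: "Summaries and analysis of acceptability variables will be presented for both the modified and per-protocol study populations". Section 7.3 defines the modified set as "all study volunteers who complied with study procedures and remained on study, per protocol, until at least the day 7 clinic visit" and the per-protocol set as "all study volunteers who complied with all protocol procedures and remained on the study until their day 14 visit". It also defines a wider population, "including all subjects who received at least a single use of RD19", which 7.4.2 does not mention.

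A separate sentence in 7.4.2 reads: "Device use and protocol procedures compliance rates will be calculated and presented". It names neither a population nor a denominator.

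Collection is wider than analysis. Section 6.2 has every subject complete the acceptability survey, and Table 3 schedules it on Days 1, 7 and 14 or at early termination. Section 5.5.3 puts the reason for any withdrawal on the e-CRF. Section 5.5.4 asks for the early-termination procedures when a subject stops using the device. On set sizes, 7.4.3 says of numbers and ratios: "Enrolled:Modified Per-Protocol and Enrolled:Per-Protocol will be presented".

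**The concern.** The endpoint asks how usable the device is and why people depart from the schedule. The subjects best placed to answer are those who struggled, stopped or were removed. Section 5.5.3 allows removal for non-compliance and for using the device in a way that does not match the instructions, so a subject who misread unclear instructions can be taken off study. Membership of either summary set then depends on having complied and stayed, which is part of the outcome itself. A subject who leaves before the Day 7 visit has Day 1 survey data that belong to neither set.

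At stake is whether the acceptability table describes everyone who used a self-administered device or only those for whom it went well. Because 'complied' is not defined, and the compliance rate has no denominator, the same behaviour could give different figures depending on choices made after the data are seen.

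**Working it through.** The documents give no expected compliance, so there is no figure of theirs to reproduce. The sizes below are illustrations.

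**Inputs from the protocol.** 25 subjects (section 4). Two uses a day (Table 2) over 14 days: 2 × 14 = 28 uses each, 25 × 28 = 700 in all.

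**Assumed inputs.** k subjects take 50% of scheduled uses and the other 25 − k take 95%. Values are shown for k = 1 and k = 5.

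**1. 'Complied' means visits and procedures only.**

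| Case | k = 1 | k = 5 |
|---|---|---|
| All users, nobody stops | (24×28×0.95 + 1×28×0.5)/700 = 652.4/700 = 93.2% | (20×28×0.95 + 5×28×0.5)/700 = 602/700 = 86.0% |
| k subjects leave at the Day 7 visit: all users, uses scheduled to the stop | (638.4 + 7)/(672 + 14) = 645.4/686 = 94.1% | (532 + 35)/(560 + 70) = 567/630 = 90.0% |
| Same, over all 700 uses | 645.4/700 = 92.2% | 567/700 = 81.0% |
| Per-protocol set, leavers excluded | 638.4/672 = 95.0% | 532/560 = 95.0% |

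- If nobody leaves, both sets equal all users and there is no distortion.
- If the k subjects leave at the Day 7 visit, the modified set still holds all 25. Only the per-protocol set loses them.
- If they leave before the Day 7 visit, both sets give 95.0%, the rate assumed for the others.
- For k = 1 the per-protocol figure exceeds the all-users figure to the stop by 95.0 − 94.1 = 0.9 points, and the no-stop value by 95.0 − 93.2 = 1.8 points. The gap of 95.0 − 92.2 = 2.8 points arises only if uses after the stop count as missed.
- For k = 5 the first two gaps are 5.0 and 9.0 points.

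**2. 'Complied' means every scheduled use (strict reading).** The per-protocol set is then 100% compliant by definition and has no missed uses to explain. The modified set is 100% to Day 7. With independent uses, the expected per-protocol size is 24 × 0.95^28 = 24 × 0.238 = 5.7 for k = 1 and 20 × 0.238 = 4.8 for k = 5. The modified set is 24 × 0.95^14 = 24 × 0.488 = 11.7 and 20 × 0.488 = 9.8. Even if all 25 took 98% or 99% of uses, the per-protocol set would be expected to hold 25 × 0.98^28 = 14.2 or 25 × 0.99^28 = 18.9.

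**3. Share of missed uses that belong to the low users.** Nobody stopped: 14/(33.6 + 14) = 29% for k = 1 and 70/(28 + 70) = 71% for k = 5. To a Day 7 stop: 7/40.6 = 17% and 35/63 = 56%. A set without these subjects loses that share of the missed uses that need a reason.

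**4. Survey items.** Suppose 90% of the others and 30% of the k subjects rate ease of use favourably (both assumed). A set without the k subjects gives 90%. All users give (24×0.9 + 1×0.3)/25 = 87.6% for k = 1 and (20×0.9 + 5×0.3)/25 = 78% for k = 5.

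**5. Sensitivity to the use count.** Devices are returned at the end of participation, so about 27 uses each, and 13 to the Day 7 visit, may be more realistic. For k = 5, uses to the stop give (20×27×0.95 + 5×13×0.5)/(540 + 65) = 545.5/605 = 90.2%. The picture is unchanged.

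**The case against.** Several counter-arguments have force.

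- **The compliance rate stands apart.** A reader might infer that the plan computes compliance among compliers and must report 100%. The text does not support that. Only the acceptability variables are tied to the two sets, and the compliance-rate sentence carries no such limit. It also names device use separately from protocol procedures, while 7.3 speaks of procedures. That favours the reading under which device use is not fixed by set membership, so the 100% figure and the small sets in step 2 belong to the less favoured reading. What stands is that an all-users rate is neither planned nor excluded.
- **Leavers' information is collected.** A reader might infer that it is lost. It is not: withdrawal reasons go on the e-CRF, and the survey is part of the early-termination visit. A subject who elects to stop need not attend that visit (5.5.2). None of these provisions places the data in the endpoint summary. The counts in 7.4.3 show how many subjects each set excludes, not how they used the device or why they stopped.
- **Stopping the device is not leaving the study.** Section 5.5.4 says so, and a subject who stops but stays might remain in the per-protocol set. The 95.0% for the Day 7 case assumes that they do not.
- **The size is assumed.** Section 7.2 expects nearly everyone to complete a short study, and one low user changes little. This limits the size of the concern. It does not justify the choice of population.

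A reader might also contrast this with safety, where "Summaries and analyses of safety data will be presented for the Safety Analysis Population". That contrast is not clean: 7.4.1 also groups the binary solicited-AE analysis by the two per-protocol sets. The point does not rest on it.

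**Conclusion.** The concern holds for the populations chosen for the acceptability variables. Sections 1.1.2, 7.3 and 7.4.2 together summarise an endpoint that includes compliance and its reasons in subjects selected for complying and staying. Early leavers and removed subjects fall out of one or both summaries. Subjects who merely miss uses do so only on the strict reading.

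A circular compliance rate is possible but not planned. Under the visits-and-procedures reading with no leavers, there is no effect. With one low user the compliance figure shifts by under about 2 points (0.9 to the stop, 1.8 against the no-stop value). It reaches 5 to 9 points only if five of 25 subjects use the device half the time and leave, for which the documents offer no support. All sizes rest on the assumed 50% and 95% use rates.

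The endpoint is descriptive and secondary in a study that tests no hypotheses. The change is worth making because it is cheap and the better population is already defined.

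**What to change.** In 7.4.2, make all subjects with at least one use, as defined in 7.3, the main population for acceptability, device-use compliance and reasons for non-compliance. Report compliance over uses scheduled up to the date device use stopped, with the number stopping early and why beside it. Give compliance over all scheduled uses as a supporting figure. In the Day 7 stop example the two figures bracket the no-stop value: 94.1% and 92.2% around 93.2% for k = 1, and 90.0% and 81.0% around 86.0% for k = 5. Keep the modified and per-protocol summaries as supplementary, and state in 7.3 whether 'complied' includes device use. The removal power in 5.5.3 needs no change.

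The cost is one or two sentences, a clarification and one extra table column, with no new visits or subjects. The reported figures may be less favourable. Whether each use and each reason is already captured cannot be checked, because the acceptability source document is not shown.
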